6.2.1.4 Step-Dosing

Pre-clinical studies of NL-201 suggest that symptomatic toxicity of NL-201 in animals peaks with the first dose, such that symptomatic toxicity caused by subsequent doses is attenuated compared to that caused by the first dose. Dose levels that are not tolerated when given as an initial dose become tolerated after giving 1 or more initial step-doses at a reduced (tolerated) dose level, and remain tolerated in subsequent doses. Thus, if a specific dose level is not well tolerated (ie, elicits DLTs in $\geq 33\%$ of patients), it is possible that tolerability can be improved by providing 1 or more reduced doses. Once the target dose is reached, subsequent doses would be given at the expected dose level for that cohort.

If step-dosing is implemented, dosing during the first cycle of step-dosing will be administered on Day 1 and Day 8 for both Schedule A and Schedule B patients, though in subsequent cycles Schedule A patients will resume Q3W dosing while Schedule B patients will continue Day 1+8 dosing.

The Cycle 1 dose used for step-dosing will be calculated as one half of the highest tolerated initial dose (HTID), ie, the highest initial dose at which $< 33\%$ of patients experience DLTs. Subsequent cycles will increase 1 dose level (DL) at a time to the CTD.

Table 10 Step-Dosing Guidance

Steps	Cycle 1				
	D1	D8	C2	C3	C4
1	0.5 x HTID	0.5 x HTID	CTD		
2	0.5 x HTID	0.5 x HTID	HTID + 1 DL	CTD	
3	0.5 x HTID	0.5 x HTID	HTID + 1 DL	HTID + 2 DL	CTD

C = cycle; CTD = cohort target dose; D = day; DL = dose level; HTID = highest tolerated initial dose

The DLT window for each patient during step-dosing will extend to include the cycle in which the patient first receives the CTD. The DLT window for each cohort is highlighted in gray in [Table 10](#).

6.2.1.5 Stopping Rules

Enrollment will be immediately suspended for any treatment-related Grade 5 toxicity. After review and discussion of all relevant data by the DMC, including benefit and risk, a proposal to amend or discontinue the study will be considered. No additional patients will be enrolled until the review has been completed, measures to improve patient safety have been implemented, and an amendment, if indicated, is approved.

6.2.2 Dosage Adjustments, Delays, Rules for Withholding or Restarting, Permanent Discontinuation

6.2.2.1 NL-201 Dosage Adjustments, Delays, Rules for Withholding or Restarting, Permanent Discontinuation

Patients that experience a DLT may be dose-reduced or withdrawn from the study after discussion with the medical monitor. The reason for dose change of NL-201 is to be recorded on each patient's case report form (CRF). Dose escalation patients and expansion patients may also experience delays, reductions and other dose adjustments. Dose may be delayed up to 21 days; any delay beyond 21 days must be approved by the medical monitor. If Cycle 2 is skipped, then PK, antitumor activity, cytokines, and PDn samples should still be collected at the next cycle according to the Cycle 2 schedule and documented as unscheduled visits.

Refer to [Table 11](#) for guidance on toxicity management and dose modifications.

For Parts 3 and 4, refer to [Section 6.2.2.2](#) for guidance on withholding NL-201 when given in combination with pembrolizumab.

Table 11 Dose Delay^a and Modification Guidance for IV Administration

Potential Toxicity	Dose Modification if Grade ≤ 2	Dose Modification if Grade ≥ 3
Chills		Hold dose until Grade ≤ 2
Fever		Hold dose until Grade ≤ 2
Pruritis		No change
Nausea/vomiting/anorexia		Hold dose until Grade ≤ 2
Diarrhea		Hold dose until Grade ≤ 2
Gastritis/stomach upset		Hold dose until Grade ≤ 2
Malaise		Hold dose until Grade ≤ 2 if other Grade ≥ 3 toxicities occur simultaneously
Anemia		Hold dose until Grade ≤ 2 or return to baseline
Leukocytosis		Hold dose until leukocyte count $< 100,000/\text{mm}^3$
Thrombocytopenia		Hold dose until Grade ≤ 2
Edema/weight gain		No change
Hypotension		Hold dose until Grade ≤ 2 , resume 1 dose level lower. Stop treatment if vasopressor support is required.
Capillary leak syndrome		Hold dose until Grade ≤ 2
Cytokine release syndrome	Hold dose until recovery to Grade 1. Pre-medication should be adjusted per Section 6.1.3 . NL-201 dosing may be resumed at the same dose.	Grade 3: Hold dose until recovery to Grade 1. Pre-medication should be adjusted per Section 6.1.3 . NL-201 dosing may be resumed at the same dose. If Grade 3 recurs and cannot be managed with supportive measures including the use of steroids with short biological half-life (eg, prednisone), dose must be reduced by one dose level for subsequent doses after discussion with Medical Monitor. Grade 4: Stop treatment
Dyspnea		Hold dose until Grade ≤ 2 , resume 1 dose level lower. Stop treatment if ventilator support is required
Oliguria		Hold dose until Grade ≤ 2 , resume 1 dose level lower
Increased creatinine		Hold dose until Grade ≤ 2 , resume 1 dose level lower if peak is Grade 3, stop treatment if peak is Grade 4.
Renal failure		Stop therapy if requires dialysis
Pleural effusion		Hold dose until Grade ≤ 2
Bowel perforation		Stop treatment
Anxiety		Hold dose until Grade ≤ 2 or back to baseline, resume 1 dose level lower

Potential Toxicity	Dose Modification if Grade ≤ 2	Dose Modification if Grade ≥ 3
Confusion		Hold dose until Grade ≤ 2, resume 1 dose level lower
Agitation or combativeness		Hold dose until Grade ≤ 2, resume 1 dose level lower
Somnolence		Hold dose until Grade ≤ 2, resume 1 dose level lower
Insomnia		No change
Arrhythmia		Hold dose until Grade ≤ 2, resume 1 dose level lower. If not resolved back to baseline within 3 weeks, or normal sinus rhythm not achieved with chemical cardioversion, stop treatment.
Elevated troponin levels		Hold dose until Grade ≤ 2, resume 1 dose level lower. If changes in left ventricular function have not improved to baseline within 3 weeks, stop treatment.
Myocardial infarction		Stop treatment
Elevated transaminases ^b		Hold dose if Grade 4 without liver metastases. If changes have not improved to baseline within 3 weeks, stop treatment.
Hyperbilirubinemia		Hold dose if Grade 4 without liver metastases. If changes have not improved to baseline within 3 weeks, stop treatment.
Electrolyte imbalances		Hold dose until Grade ≤ 2
Neutropenia		Hold dose until Grade ≤ 2, resume 1 dose lower if ANC < 500 for ≥ 5 days
Febrile neutropenia		Stop treatment
Infusion-related reaction or hypersensitivity reaction	Stop infusion immediately. Consider treatment with diphenhydramine and/or acetaminophen. Infusion may be resumed after Grade 2 reaction has resolved with slower infusion rate. Pre-medication should be adjusted per Section 6.1.3 .	Grade 3: Consider treatment with diphenhydramine and/or acetaminophen and/or systemic steroids per institutional standard practice. If infusion reaction occurs and it can be adequately managed with supportive measures, the patient may be continued on the study with pre-medication adjusted per Section 6.1.3 for subsequent doses. Otherwise, stop treatment. If Grade 3 recurs and cannot be managed with supportive measures including steroids, dose must be reduced by 1 dose level for subsequent doses. Grade 4: Stop treatment

ANC = absolute neutrophil count; IV = intravenous.

a Dose may be delayed up to 21 days; any delay longer than 21 days must be approved by medical monitor

b Refer to [Section 10.5](#) if drug-induced liver injury is suspected.

6.2.2.2 Pembrolizumab Dosage Adjustments, Delays, Rules for Withholding or Restarting, Permanent Discontinuation

6.2.2.2.1 Dose Modification and Toxicity Management for Immune-Related AEs Associated with Pembrolizumab

AEs associated with pembrolizumab combination exposure, including coadministration with additional compounds may represent an immune-related response. These irAEs may occur shortly after the first dose or several months after the last dose of pembrolizumab combination treatment and may affect more than one body system simultaneously. Therefore, early recognition and initiation of treatment is critical to reduce complications. Based on existing clinical study data, most irAEs were reversible and could be managed with interruptions of pembrolizumab combination treatment, administration of corticosteroids and/or other supportive care. For suspected irAEs, ensure adequate evaluation to confirm etiology or exclude other causes. Additional procedures or tests such as bronchoscopy, endoscopy, skin biopsy may be included as part of the evaluation. Dose modification and toxicity management guidelines for irAEs associated with pembrolizumab are provided in [Table 12](#).

Attribution of Toxicity:

When study interventions are administered in combination, attribution of an AE to a single component is likely to be difficult. Therefore, while the investigator may attribute a toxicity event to the combination, to NL-201 alone, or to pembrolizumab alone, for AEs listed in [Table 12](#), both interventions must be held according to the criteria in [Table 12](#).

Holding Study Interventions:

When study interventions are administered in combination, if the AE is considered immune-related, both interventions should be held according to recommended dose modifications.

Restarting Study Interventions:

Participants may not have any dose modifications (no change in dose or schedule) of pembrolizumab in this study, as described in [Table 12](#).

If the toxicity does not resolve or the criteria for resuming treatment are not met, the participant must be discontinued from all study interventions.

If the toxicities do resolve and conditions are aligned with what is defined in [Table 12](#), the combination of NL-201 and pembrolizumab may be restarted at the discretion of the investigator. In these cases where the toxicity is attributed to the combination or to NL-201 alone, re-initiation of pembrolizumab as a monotherapy may be considered after communication with and agreement by the Sponsor.

Table 12 Dose Modification and Toxicity Management Guidelines for Immune-Related Adverse Events Associated with Pembrolizumab

General instructions:				

 Severe and life-threatening irAEs should be treated with IV corticosteroids followed by oral steroids. Other immunosuppressive treatment should begin if the irAEs are not controlled by corticosteroids. Pembrolizumab must be permanently discontinued if the irAE does not resolve or the corticosteroid dose is not ≤ 10 mg/day within 12 weeks of the last pembrolizumab-treatment. The corticosteroid taper should begin when the irAE is \leq Grade 1 and continue at least 4 weeks. If pembrolizumab has been withheld, pembrolizumab may resume after the irAE decreased to \leq Grade 1 after corticosteroid taper. 				
irAEs	Toxicity grade (CTCAE V5.0)	Action with pembrolizumab	Corticosteroid and/or other therapies	Monitoring and follow-up
Pneumonitis	Grade 2	Withhold	Administer corticosteroids (initial dose of 1 to 2 mg/kg prednisone or equivalent) followed by taper	Monitor participants for signs and symptoms of pneumonitis Evaluate participants with suspected pneumonitis with radiographic imaging and initiate corticosteroid treatment
	Recurrent Grade 2, Grade 3 or 4	Permanently discontinue	Add prophylactic antibiotics for opportunistic infections	
Diarrhea/Colitis	Grade 2 or 3	Withhold		Monitor participants for signs and symptoms of enterocolitis (ie, diarrhea, abdominal pain, blood or mucus in stool with or without fever) and of bowel perforation (ie, peritoneal signs and ileus) Participants with \geq Grade 2 diarrhea suspecting colitis should consider GI consultation and performing endoscopy to rule out colitis
	Recurrent Grade 3 or Grade 4	Permanently discontinue	Administer corticosteroids (initial dose of 1 to 2 mg/kg prednisone or equivalent) followed by taper	Participants with diarrhea/colitis should be advised to drink liberal quantities of clear fluids. If sufficient oral fluid intake is not feasible, fluid and electrolytes should be substituted via IV infusion

AST or ALT elevation or Increased Bilirubin	Grade 2 ^a	Withhold	Administer corticosteroids (initial dose of 0.5 to 1 mg/kg prednisone or equivalent) followed by taper	Monitor with liver function tests (consider weekly or more frequently until liver enzyme value returned to baseline or is stable)
	Grade 3 ^b or 4 ^c	Permanently discontinue	Administer corticosteroids (initial dose of 1 to 2 mg/kg prednisone or equivalent) followed by taper	
Type 1 diabetes mellitus (T1DM) or Hyperglycemia	New onset T1DM or Grade 3 or 4 hyperglycemia associated with evidence of β -cell failure	Withhold ^d	Initiate insulin replacement therapy for participants with T1DM Administer antihyperglycemic in participants with hyperglycemia	Monitor participants for hyperglycemia or other signs and symptoms of diabetes
Hypophysitis	Grade 2	Withhold	Administer corticosteroids and initiate hormonal replacements as clinically indicated	Monitor for signs and symptoms of hypophysitis (including hypopituitarism and adrenal insufficiency)
	Grade 3 or 4	Withhold or permanently discontinue ^d		
Hyperthyroidism	Grade 2	Continue	Treat with nonselective beta-blockers (eg, propranolol) or thionamides as appropriate	Monitor for signs and symptoms of thyroid disorders
	Grade 3 or 4	Withhold or permanently discontinue ^d		
Hypothyroidism	Grade 2, 3 or 4	Continue	Initiate thyroid replacement hormones (eg, levothyroxine or liothyronine) per standard of care	Monitor for signs and symptoms of thyroid disorders
Nephritis: grading according to increased creatinine or acute kidney injury	Grade 2	Withhold	Administer corticosteroids (prednisone 1 to 2 mg/kg or equivalent) followed by taper	Monitor changes of renal function
	Grade 3 or 4	Permanently discontinue		
Neurological Toxicities	Grade 2	Withhold	Based on severity of AE administer corticosteroids	Ensure adequate evaluation to confirm etiology and/or exclude other causes
	Grade 3 or 4	Permanently discontinue		

Myocarditis	Grade 2, 3 or 4	Permanently discontinue	Based on severity of AE administer corticosteroids	Ensure adequate evaluation to confirm etiology and/or exclude other causes
Exfoliative Dermatologic Conditions	Suspected SJS, TEN, or DRESS	Withhold	Based on severity of AE administer corticosteroids	Ensure adequate evaluation to confirm etiology or exclude other causes
	Confirmed SJS, TEN, or DRESS	Permanently discontinue		
All Other irAEs	Persistent Grade 2	Withhold	Based on severity of AE administer corticosteroids	Ensure adequate evaluation to confirm etiology or exclude other causes
	Grade 3	Withhold or discontinue based on the event ^e		
	Recurrent Grade 3 or Grade 4	Permanently discontinue		

AE(s) = adverse event(s); ALT = alanine aminotransferase; AST = aspartate aminotransferase; CTCAE = Common Terminology Criteria for Adverse Events; DRESS = drug reaction with eosinophilia and systemic symptoms; GI = gastrointestinal; ir = immune related; IV = intravenous; SJS = Stevens-Johnson Syndrome; T1DM = type 1 diabetes mellitus; TEN = Toxic Epidermal Necrolysis; ULN = upper limit of normal.

Note: Non-irAE will be managed as appropriate, following clinical practice recommendations.

- a AST/ALT: >3.0 to 5.0 x ULN if baseline normal; >3.0 to 5.0 x baseline, if baseline abnormal; bilirubin:>1.5 to 3.0 x ULN if baseline normal; >1.5 to 3.0 x baseline if baseline abnormal
- b AST/ALT: >5.0 to 20.0 x ULN, if baseline normal; >5.0 to 20.0 x baseline, if baseline abnormal; bilirubin:>3.0 to 10.0 x ULN if baseline normal; >3.0 to 10.0 x baseline if baseline abnormal
- c AST/ALT: >20.0 x ULN, if baseline normal; >20.0 x baseline, if baseline abnormal; bilirubin: >10.0 x ULN if baseline normal; >10.0 x baseline if baseline abnormal
- d The decision to withhold or permanently discontinue pembrolizumab is at the discretion of the investigator or treating physician. If control achieved or ≤ Grade 2, pembrolizumab may be resumed.
- e Events that require discontinuation include but are not limited to: encephalitis and other clinically important irAEs (eg, vasculitis and sclerosing cholangitis).

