- The Investigator will collect pregnancy information on any female patient who becomes pregnant while participating in this study. Information will be recorded on the appropriate form and submitted to the Sponsor within 24 hours of learning of a patient's pregnancy.
- The patient will be followed to determine the outcome of the pregnancy. The Investigator will collect follow-up information on the patient and the neonate and the information will be forwarded to the Sponsor. Generally, follow-up will not be required for longer than 6 to 8 weeks beyond the estimated delivery date. Any termination of pregnancy will be reported, regardless of fetal status (presence or absence of anomalies) or indication for the procedure.

- A spontaneous abortion (occurring at < 22 weeks gestational age) or still birth (occurring at > 22 weeks gestational age) is always considered to be an serious adverse event (SAE) and will be reported as such.
- Any post-study pregnancy-related SAE considered reasonably related to the study drug by the Investigator will be reported to the Sponsor as described in **Section 8.4.5** and **Section 8.4.6**. While the Investigator is not obligated to actively seek this information in former study patients, he or she may learn of an SAE through spontaneous reporting.
- Any female patient who becomes pregnant while participating in the study will discontinue study drug or be withdrawn from the study.

10.5 Appendix 5: Liver Safety: Suggested Actions and Follow-Up Assessments and Study Drug Rechallenge Guidelines

Patients with abnormal hepatic laboratory values (ie, aspartate aminotransferase [AST], alanine aminotransferase [ALT], total bilirubin [TBL]) and/or international normalized ratio (INR) and/or signs/symptoms of hepatitis may meet the criteria for withholding or permanent discontinuation of NL-201, as specified in the Guidance for Industry Drug-Induced Liver Injury: Premarketing Clinical Evaluation, July 2009.

The following stopping and/or withholding rules apply to patients for whom another cause of their changes in liver biomarkers (TBL, INR, and transaminases) has not been identified.

Important alternative causes for elevated AST/ALT and/or TBL values include, but are not limited to:

- hepatobiliary tract disease
- viral hepatitis (eg, hepatitis A/B/C/D/E, Epstein-Barr Virus, cytomegalovirus, herpes simplex virus, varicella, toxoplasmosis, and parvovirus)

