- right-sided heart failure, hypotension or any cause of hypoxia to the liver causing ischemia
- exposure to hepatotoxic agents/drugs or hepatotoxins, including herbal and dietary supplements, plants and mushrooms
- heritable disorders causing impaired glucuronidation (eg, Gilbert's syndrome, Crigler-Najjar syndrome) and drugs that inhibit bilirubin glucuronidation (eg, indinavir, atazanavir)
- α -1 antitrypsin deficiency
- alcoholic hepatitis
- autoimmune hepatitis
- Wilson's disease and hemochromatosis
- nonalcoholic fatty liver disease including steatohepatitis
- non-hepatic causes (eg, rhabdomyolysis, hemolysis)

Liver Chemistry Stopping Criteria – Liver Stopping Event	
ALT or AST-absolute	alanine aminotransferase (ALT) or aspartate aminotransferase (AST) \geq 5x the upper limit of normal (ULN)
ALT or AST increase	ALT or AST \geq 3 x ULN persists for \geq 4 weeks
Bilirubin^{a,b}	ALT or AST \geq 3 x ULN and total bilirubin \geq 2 x ULN (> 35% direct bilirubin)
INR²	ALT or AST \geq 3 x ULN and international normalized ratio (INR) > 1.5
Cannot monitor	ALT or AST \geq 3 x ULN and cannot be monitored weekly for 4 weeks
Symptomatic^c	ALT or AST \geq 3 x ULN associated with symptoms (new or worsening) believed to be related to liver injury or hypersensitivity

Required Actions, Monitoring, and Follow up Assessments	
Actions	Follow-up Assessments

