
 • Immediately discontinue study drug. • Report the event to PPD within 24 hours • Complete the reporting form and complete a serious adverse event (SAE) data collection tool if the event also met the criteria for an SAE.^b • Perform liver chemistry follow-up assessments as described in the Follow-up Assessment column. • Do not restart or rechallenge patient with study drug • Monitor the patient until liver chemistry test abnormalities resolve, stabilize, or return to baseline (see MONITORING). 
MONITORING:
 
If ALT ≥ 3 x ULN AND total bilirubin ≥ 2 x ULN OR INR > 1.5:
 
 • Repeat liver chemistry tests (include ALT, AST, alkaline phosphatase, total bilirubin, and INR) and perform liver event follow-up assessments within 24 hours. • Monitor patient twice weekly until liver chemistry test abnormalities resolve, stabilize, or return to baseline. • A specialist or hepatology consultation is recommended. 
If ALT ≥ 3 x ULN AND total bilirubin < 2 x ULN AND INR ≤ 1.5:
 
 • Perform liver chemistry tests (include ALT, AST, alkaline phosphatase, total bilirubin and INR) and perform liver chemistry follow-up assessments within 24 to 72 hours. • Monitor patients weekly until liver chemistry abnormalities resolve, stabilize, or return to baseline. • Do not restart/rechallenge patient with NL-201 unless allowed per protocol and Neoleukin approval is granted 	
 • Viral hepatitis serology^c • Obtain INR and recheck with each liver chemistry assessment until the transaminases values show downward trend • Obtain blood sample for pharmacokinetic (PK) analysis after the most recent dose^d • Obtain serum creatine phosphokinase (CPK), lactate dehydrogenase (LDH), gamma-glutamyl transferase (GGT), glutamate dehydrogenase (GLDH) and serum albumin • Fractionate bilirubin, if total bilirubin ≥ 2 xULN • Obtain complete blood count with differential to assess eosinophilia • Record the appearance or worsening of clinical symptoms of liver injury, or hypersensitivity, on [liver event/expedited reporting form] • Record use of concomitant medications (including acetaminophen, herbal remedies, recreational drugs and other over-the-counter medications) • Record alcohol use on the [liver event alcohol intake form]. 
If ALT ≥ 3 x ULN AND total bilirubin ≥ 2 x ULN OR INR > 1.5 obtain the following in addition to the assessments listed above:
 
 • Anti-nuclear antibody, anti-smooth muscle antibody, Type 1 anti-liver kidney microsomal antibodies, and quantitative total immunoglobulin G (IgG) or gamma globulins. • Serum acetaminophen adduct assay, when available, to assess potential acetaminophen contribution to liver injury in patients with definite or likely acetaminophen use in the preceding week. Liver imaging (ultrasound, magnetic resonance, or computerized tomography) and/or liver biopsy to evaluate liver disease • Liver biopsy may be considered and discussed with local specialists if available for instance: 
 ○ In patients when serology raises the possibility of autoimmune hepatitis (AIH) ○ In patients when suspected drug-induced liver injury (DILI) progresses or fails to resolve on withdrawal of study drug ○ In patients with acute or chronic atypical presentation.

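### Parts 1 and 2: Table 11 and Appendix 5 give conflicting instructions for unexplained ALT/AST ≥ 5 × ULN, and no text says which takes precedence

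*Combined protocol and SAP*

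**What the plan says.** Table 11, elevated transaminases, Grade ≥ 3 column: "Hold dose if Grade 4 without liver metastases. If changes have not improved to baseline within 3 weeks, stop treatment". The Grade ≤ 2 cell is blank. Footnote b on this row refers the reader to Section 10.5 "if drug-induced liver injury is suspected".

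Section 10.5 (Appendix 5) defines its own scope. Its stopping or withholding "rules apply to patients for whom another cause of their changes in liver biomarkers (TBL, INR, and transaminases) has not been identified". Its list of liver stopping events includes ALT or AST ≥ 5 × ULN with no further condition. The actions are "Immediately discontinue study drug" and "Do not restart or rechallenge patient with study drug". A later line covers ALT ≥ 3 × ULN with bilirubin < 2 × ULN and INR ≤ 1.5: "Do not restart/rechallenge patient with NL-201 unless allowed per protocol and Neoleukin approval is granted".

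The labels point in different directions. Section 6.2.2.1 describes Table 11 as guidance. Appendix 5 is titled "Liver Safety: Suggested Actions and Follow-Up Assessments and Study Drug Rechallenge Guidelines", yet the heading of its action table calls the actions required. Section 7.1 refers to Section 6.2.2 for toxicities that require permanent discontinuation and does not name Section 10.5.

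**The concern.** The same laboratory value in the same patient leads to different actions depending on which page the site opens. Table 5 names hepatotoxicity as a risk, and this is a first-in-human study.

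Footnote b would remove the conflict if its trigger matched that of Appendix 5, but it does not. Footnote b needs a positive suspicion of drug injury. Appendix 5 needs only that no other cause has been found. The gap is realistic during work-up. Appendix 5 lists hypotension and exposure to hepatotoxic drugs among the alternative causes. Hypotension has its own row in Table 11, and Section 6.1.3 requires an antipyretic such as acetaminophen before monotherapy doses of 0.6 µg/kg or more. An investigator may lean towards one of these causes without having established it. Appendix 5 then applies, while footnote b arguably does not.

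At stake is whether a patient whom Appendix 5 would take off treatment is instead held and resumed, or dosed again.

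**Working it through.** The plan gives no figure to reproduce. The check sets the two rules side by side and then looks at the visit calendar.

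**Inputs.** Table 11 row and footnote b (Section 6.2.2.1). Scope, threshold and actions in Section 10.5. ALT/AST grade limits for a normal baseline, from the footnotes to Table 12: Grade 2 is > 3 to 5 × ULN, Grade 3 is > 5 to 20 × ULN, Grade 4 is > 20 × ULN. Schedule B visits from Table 2. Part 1 DLT definition from Section 6.2.1.3.

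**Step 1: same value, two rules (normal baseline, no other cause identified).**

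| ALT/AST | Grade | Table 11 row | Section 10.5 |
|---|---|---|---|
| exactly 5 × ULN | 2 | blank | discontinue at once |
| > 5 to 20 × ULN | 3 | no hold stated | discontinue at once |
| > 20 × ULN, no liver metastases | 4 | hold; stop only if not back to baseline within 3 weeks | discontinue at once |

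The rules differ at every value from 5 × ULN upward. The 3-week sentence sits in the Grade ≥ 3 column, so it could be read to cover Grade 3 as well. Even then, no hold at Grade 3 is ordered.

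**Step 2: can the row be confined to explained rises?** That reading would remove the conflict. The row's wording works against it, because its only hold applies where liver metastases, an obvious alternative cause, are absent. It therefore overlaps the population that Appendix 5 addresses.

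**Step 3: timing in Schedule B, Cycle 1.** Chemistry is drawn on Day 4 (window 0) and Day 8 (± 1), and NL-201 is given on Days 1 and 8.

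- Day 4 result to Day 8 dose: 7 − 4 = 3, 8 − 4 = 4, 9 − 4 = 5 days.
- First dose to the latest Day 8 dose: 9 − 1 = 8 days. Under the pandemic window in Table 5 (Day 8 plus 5 days) it is 13 − 1 = 12 days.

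The Part 1 DLT for a Grade ≥ 3 ALT/AST rise needs at least 14 days, so it cannot have been met by the Day 8 dose. Day 4 chemistry again precedes a Day 8 dose in Cycle 2.

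**Step 4: other checks.** Section 8 and Table 2 require laboratory limits to be confirmed before dosing on C1D1 only. Under Section 8.4.2 an isolated ALT/AST rise is not an event of clinical interest. The 24-hour liver-event report sits inside Appendix 5, so it helps only a site already using that appendix.

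**The case against.** The strongest reply is that the protocol already contains the rule. Footnote b is attached to the row in question. Appendix 5 is framed around drug-induced liver injury and applies on its own terms, without needing the footnote. Most investigators would regard an unexplained rise on a drug with a named liver risk as suspected drug injury. This stands: the coherent reading is that Appendix 5 governs, and a site reading it that way stops.

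Three stronger inferences might tempt a reader, and the documents do not support them.

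- *Table 11 orders redosing at Grade 3.* It does not. It is silent there, and redosing would need a site to read silence as permission.
- *Section 7.1 bypasses Appendix 5.* It does not. Section 7.1 leads to Section 6.2.2, which holds Table 11, whose footnote b cites Section 10.5. Its list of reasons is also open.
- *Nothing else would intervene.* Section 8 asks for immediate safety concerns to be discussed with the sponsor. Section 8.3.4 requires documented laboratory review and repeat of clinically significant values. Section 8.4.2 provides for consultation with the sponsor on liver tests below the event-of-clinical-interest threshold. Schedule B also has pre-dose chemistry on Day 8.

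These provisions lower the risk. None of them says which rule applies, and the difference in triggers remains.

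**Conclusion.** Wrong as written, and minor in size. For unexplained ALT/AST ≥ 5 × ULN in Parts 1 and 2, two stated safety rules conflict and no text gives precedence. The practical exposure is a site that has found no other cause, does not yet suspect the drug, and works from the Table 11 row.

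The number of patients affected cannot be stated, because the documents give no incidence of such rises. The timing in Step 3 shows only that a Day 8 dose could fall between an Appendix 5 trigger and any DLT.

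The conclusion assumes a normal baseline and that the grade limits printed under Table 12 also apply to Table 11. It does not extend to Parts 3 and 4, where Section 6.2.2.2.1 applies the Table 12 criteria to both drugs. Nor is the Appendix 5 bar on restarting absolute: an isolated rise with bilirubin < 2 × ULN and INR ≤ 1.5 falls under its conditional line. The firm contrast is therefore immediate discontinuation against no stated hold, or against a hold with possible resumption.

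**What to change.** Reword footnote b along these lines: *If a Section 10.5 liver stopping criterion is met and another cause has not been identified, Section 10.5 takes precedence over this row: discontinue NL-201; any rechallenge only as Section 10.5 allows.* The last clause leaves both Appendix 5 conditions on restart in place, namely protocol allowance and sponsor approval, and creates no new permission.

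Also cite Section 10.5 beside Section 6.2.2 in the Section 7.1 discontinuation bullet, and make the Appendix 5 title agree with its table on whether the actions are suggested or required.

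The cost is protocol wording only. There may be a few more discontinuations for transient Grade 3 rises, but Appendix 5 already requires these. Patients with liver metastases and raised baseline ALT/AST are a separate question that this wording does not settle.
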